6.4 STUDY INTERVENTION COMPLIANCE

- Approximately the 1st half of study duration will be in the later weeks of the NICU admission. During this time, compliance with protocol requirements will be closely monitored by research staff and documented in the database.

- To maximize compliance with study protocol during the several weeks at home, families will be instructed in all aspects of protocol adherence while in the NICU, and reinforced just prior to discharge.
- Once discharged, research staff will contact each family within the first 2-3 days home to address parental concerns or questions, and encourage compliance with study procedures. Staff will re-contact each family at least weekly thereafter to support families and encourage full home compliance with protocol requirements.
- Two salivary caffeine concentrations will be obtained in all subjects. Although results will not be available until the end of the study, the results will be useful in analyses to assess adherence to the administration of study drug, and understand the relationship between caffeine concentrations and study safety and efficacy outcomes.

6.5 CONCOMITANT THERAPY

Uniform treatment guidelines for routine treatment caffeine have been developed for the study and agreed to by sites. The Clinical Guidelines for Routine Caffeine Use in NICU (Prior to enrollment in ICAF) include: For infants with birth weight < 1250 grams, initiate caffeine treatment within the first 3 days after birth in all infants. If on CPAP only: initiate caffeine treatment within the first 24 hours. If approaching extubation in first 3 days after birth prior to any caffeine treatment, initiate caffeine treatment 6 to 8 hours prior to extubation. For infants with birth weight \geq 1250 grams, if on CPAP or on no respiratory support, initiate caffeine treatment if the infant experiences >6 apnea episodes requiring stimulation. If the infant requires mechanical ventilation, consider starting caffeine treatment prior to extubation. The initial caffeine dose is a 20 mg/kg bolus dose of caffeine citrate (or equivalent caffeine base) followed by 5-10 mg/kg/day maintenance dose, beginning 24 hours after the loading dose. Levels are not required to monitor for dosage adjustment. Stop routine caffeine treatment once the infant is free of clinically significant episodes of apnea for 5-7 days off of any positive pressure (CPAP or NC > 1L) or at 34 weeks PMA, whichever comes first. If the maintenance dose is less than 5 mg/kg, infants may be allowed to “outgrow” their dose of caffeine and the dose should be stopped as noted above (i.e. no clinically significant episode for 5-7 days off any positive pressure (CPAP or NC > 1L) or 34 weeks PMA, whichever comes first.) Following randomization, open label caffeine use is discouraged, however, there are no prohibited therapies and sites will manage all participants based on their best clinical judgment, with guidance as needed by the an ICAF Principal Investigator.

6.5.1 RESCUE MEDICINE

As noted above, rescue therapy with open-label caffeine therapy is discouraged. Recurrent apnea-related symptoms have not occurred in preliminary studies after stopping routine caffeine.^{18,90} However, in the event that an infant has apnea-related clinical symptoms after stopping routine caffeine and starting study drug, study drug should be continued, and if judged to be needed by the clinical team, nasal CPAP or nasal cannula is the preferred additional therapy. If the clinical team ultimately decides that open-label caffeine must be used, we suggest the following: 1) Hold study drug; 2) begin open-label maintenance caffeine citrate at 5-10 mg/kg/day on the same day; 3) as soon as open-label caffeine is no longer deemed necessary, stop open-label caffeine and restart study drug at the next regularly scheduled time for study drug; 4) there should be no need to unblind the treatment group, since published studies have suggested that it is safe to give the suggested dose of open-label caffeine to either treatment group.³ If the attending physician thinks unblinding may be needed they should contact the clinical site principal investigators.

Pulse oximeter recordings will continue through hospital discharge, or at home through 1 week following discontinuation of study drug, for infants recruited at sites participating in home oximeter recording. The PMA at which study drug is scheduled to end is well after the clinical team judged it safe to stop routine caffeine treatment and at a PMA at which prior studies have shown that the extent of IH no longer differs from healthy infants born at term. However, **for sites continuing oximeter recordings at home**, the oximeter alarms may be activated for this final study week if deemed necessary by the clinical site principal investigators.

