Endpoints:	
Primary:
 
 • Extent of IH as measured by seconds below 90% saturation per 24 hours of recorded oximetry data within each week PMA, and overall • Plasma concentration changes in inflammatory biomarkers between baseline and 38 weeks + 0 days PMA • MRI changes in microstructural measures between baseline and end of study (between 43 weeks + 0 days and 46 weeks + 6 days PMA). 
Secondary
 
 • #IH events per 24 hours of recorded oximetry data, # sec < 80% saturation per 24 hours of recorded oximetry data, nadir saturation during events, and the duration of events and area under of curve during events below 90% and 80% threshold saturation • Changes in inflammatory biomarkers and MRI measures of regional tissue volume between baseline and end of study in relation to IH measures
Study Population:	
Sample size: 220 infants, 110 caffeine and 110 placebo-treated
 
Gender: Male and female
 
Age: Enrollment at PMA 32 weeks + 0 days - 36 weeks + 6 days
 
Demographic Group: Infants born at \leq30 weeks + 6 days gestation
 
General Health Status: Clinically stable, on caffeine treatment and expected to receive last dose of routine caffeine treatment no later than 36 weeks + 5 days PMA
 
Geographic location: NICU or step down unit at a participating hospital, with final weeks at home following NICU discharge

Phase:	Not applicable
Description of Sites/Facilities Enrolling Participants:	Neonatal Intensive Care Units (NICU) in hospitals in metropolitan areas in the U.S. While inpatient the research will take place in the hospital. Once discharged, if the subject has been enrolled at a site performing MRIs, the patient will return to specified outpatient locations for performance of the follow-up MRI. At the end of the study, study termination procedures will be performed in a manner convenient for the family, and may be performed in person or remotely, and if applicable may be performed at the time of an MRI.
Description of Study Intervention:	Enrolled infants will be randomized to receive caffeine or equal volume placebo. The caffeine base dose will be 5 mg/kg once daily when the infant is at age 35 weeks + 6 days PMA or less. When the infant is at 36 weeks + 0 days PMA or more the caffeine base dose will be 5 mg/kg twice daily, based on the expected increased rate of caffeine metabolism that occurs as infants age.

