4.3 JUSTIFICATION FOR DOSE

Infants will be started on oral caffeine base at 5 mg/kg/day or equivalent volume of placebo. At 36 weeks + 0 days PMA, study drug dose will be increased to 5 mg/kg BID (total daily dose 10 mg/kg) or equivalent volume of placebo. The dose will be weight-adjusted weekly until NICU discharge. The starting dose and dose escalation at 36 weeks + 0 days PMA reflect increasing clearance rates that have been established in pilot studies as being appropriate to achieve caffeine levels within the most likely therapeutic range. All subjects will be on enteral medications when enrolled.

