5.3 LIFESTYLE CONSIDERATIONS

- Parents and clinical care providers will be asked to avoid exposure to caffeine for subjects.
- Open label treatment with a methylxanthine will be documented.
- There will be no restrictions on maternal diet even if breast feeding.

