6.2.2 DOSE PREPARATION, AND LABELING

Inpatient Doses: *Caffeine base or Placebo*

Caffeine base: IDS pharmacies will prepare a bulk oral solution containing caffeine base (anhydrous) 10 mg/mL, according to the instructions in the Pharmacy Manual. A bulk solution can be prepared individually for a patient or can be used for multiple patients (preferred) who are assigned/randomized to receive active treatment.

A 24 hour supply is prepared from the bulk solution and dispensed in a suitable-sized unit-dose, oral syringe. All oral syringes prepared and administered in the inpatient setting are to be labeled in a blinded fashion, using specific departmental procedures for labeling of blinded syringes and reflecting blinded

study drug information on the medication administration record (e.g. eMAR). All syringes must be labeled as “For Investigational Use Only” (or alternative site specific verbiage to identify a study medication). Syringes can be prepared as long as 4 days prior to administration (BUD 4 days) and should be stored at room temperature.

Example: Caffeine base 10 mg/1 mL or Placebo; Caffeine base 10 mg or placebo (1 mL)

Placebo: Research pharmacies will prepare a bulk oral solution according to instructions in the pharmacy manual. A bulk solution can be prepared individually for a patient or can be used for multiple patients (preferred) who are assigned/randomized to receive placebo treatment.

A 24 hour supply is prepared from the bulk solution and dispensed in a suitable-sized unit-dose, oral syringe. All oral syringes prepared and administered in the inpatient setting are to be labeled in a blinded fashion, using specific departmental procedures for labeling of blinded syringes and reflecting blinded study drug information on a medication administration record (e.g. eMAR). All syringes must be labeled as “For Investigational Use Only” (or alternative site specific verbiage to identify a study medication). Syringes can be prepared as long as 4 days prior to administration (BUD 4 days) and should be stored at room temperature.

Example: Caffeine base 10 mg/1 mL or Placebo; Caffeine base 10 mg or placebo (1 mL)

Outpatient Doses:

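### Rescue caffeine is written as citrate and study drug as base, so the suggested switch lowers an active-arm infant's nominal caffeine dose, by about 50-75% from 36+0 at an assumed 2:1 conversion

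*Combined protocol and SAP*

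**What the plan says.** **Study drug is caffeine base.** In Section 1.1 (Description of Study Intervention), up to 35+6, "The caffeine base dose will be 5 mg/kg once daily"; from 36+0, "the caffeine base dose will be 5 mg/kg twice daily". Section 4.3 gives the same step: "study drug dose will be increased to 5 mg/kg BID (total daily dose 10 mg/kg". Section 6.2.2 confirms the form: "IDS pharmacies will prepare a bulk oral solution containing caffeine base (anhydrous) 10 mg/mL". Sections 1.1 and 4.3 explain the step-up by caffeine metabolism or clearance rising with age, and Section 4.3 links the doses to reaching likely therapeutic levels.

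**Open-label caffeine is written as citrate.** Section 6.5.1 discourages it. For apnea-related symptoms it first has study drug continued, with nasal CPAP or cannula as the preferred addition. Only if the team still concludes that open-label caffeine is required does it suggest a sequence: "1) Hold study drug", then "begin open-label maintenance caffeine citrate at 5-10 mg/kg/day on the same day", and a return to study drug once open-label caffeine is no longer needed. The fourth step, which covers both arms, says "there should be no need to unblind the treatment group, since published studies have suggested that it is safe to give the suggested dose".

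**Conversion and recording.** No section gives a citrate-to-base factor. Section 6.5 (routine caffeine before enrollment) refers to a citrate loading dose or its base equivalent, so the protocol does not treat the two as equal milligram for milligram. Section 5.3 says: "Open label treatment with a methylxanthine will be documented".

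**The concern.** The two regimens carry similar-looking numbers in different units. A blinded team that turns to open-label caffeine intends to give more caffeine. In a placebo infant the switch does that. In an active-arm infant from 36+0 it replaces the study dose with a smaller amount of caffeine, at the age when the protocol says clearance has risen enough to justify a doubled dose.

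The team could not see this happening. Treatment is blinded, and under Section 6.3 salivary caffeine results stay blinded until all infants have finished. The fourth step of Section 6.5.1 reassures sites about giving too much and does not mention giving less. What is at stake is the clarity of an instruction to blinded staff caring for symptomatic preterm infants, and its consistency with the protocol's own dose rationale.

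**Working it through.** **Inputs from the documents**
- Study drug before 36+0: 5 mg/kg/day base (Section 1.1).
- Study drug from 36+0: 5 mg/kg twice daily as base. 5 x 2 = 10 mg/kg/day, which reproduces the total daily dose in Section 4.3.
- Suggested rescue: 5-10 mg/kg/day citrate, replacing study drug (Section 6.5.1).

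**Assumption not in the documents.** Let f be mg of base per mg of citrate.
- Molecular weights with anhydrous citric acid: 194.19 / (194.19 + 192.12) = 0.503.
- With citric acid monohydrate: 194.19 / (194.19 + 210.14) = 0.480.
- Working value f = 0.5, with a range up to f = 1 (salt form ignored).

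**Rescue in base units at f = 0.5:** 5 x 0.5 = 2.5 and 10 x 0.5 = 5.0 mg/kg/day.

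**Nominal reduction in the active arm** = 1 - (citrate dose x f) / (study-drug base dose).

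| f | From 36+0, rescue 5 | From 36+0, rescue 10 | Before 36+0, rescue 5 | Before 36+0, rescue 10 |
|---|---|---|---|---|
| 0.48 | 76.0% | 52.0% | 52.0% | 4.0% |
| 0.50 | 75.0% | 50.0% | 50.0% | 0% |
| 0.503 | 74.9% | 49.7% | 49.7% | -0.5% |
| 0.60 | 70.0% | 40.0% | 40.0% | -20.0% |
| 1.00 | 50.0% | 0% | 0% | -100.0% |

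A negative value is an increase. From 36+0, no factor up to 1 puts any part of the rescue range above the active-arm study dose.

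**Placebo arm at f = 0.5:** from 0 to 2.5-5.0 mg/kg/day base.

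**Two things that make the actual change smaller than the nominal one**
- *Day of switch.* If one of the two daily doses has already been given, that day's total is 5 + 2.5 = 7.5 to 5 + 5 = 10 mg/kg base, a reduction of 25% to 0%. Section 6.1.2 notes caffeine's relatively long half-life, so exposure falls gradually.
- *At home.* Study drug is weight-adjusted only until discharge (Sections 1.3 and 4.3). If weight had since risen by 25% (an illustrative assumption), study drug would be 10 / 1.25 = 8 mg/kg/day. Rescue at current weight would then be a reduction of 1 - 5/8 = 37.5% to 1 - 2.5/8 = 69%.

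**The case against.** The strongest reply is that this is the last step of a discouraged pathway. Section 6.5.1 offers it as a suggestion, Section 6.5 leaves sites to their clinical judgment with guidance available from a trial principal investigator, and a route to request unblinding exists. Sections 2.2.1 and 6.5.1 report that recurrent apnea-related symptoms were not seen in preliminary studies. All of this stands. It limits how often the issue arises, but the instruction remains unclear when it does.

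A second reply is that Section 4.3 calls the study doses appropriate and nowhere says a lower dose is ineffective, and that the rescue range has the same numbers as routine maintenance in Section 6.5. That also stands. It is why the passages are better described as unreconciled than as a proven clinical error. It does not show that a step down from 36+0 was considered.

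Several stronger readings are tempting, and the documents do not support them:
- *Caffeine is cut whenever apnea symptoms occur.* Section 6.5.1 says to continue study drug at that stage; the hold comes only with the decision to use open-label caffeine.
- *The reduction is always more than half.* At the top of the rescue range it is about half (49.7% to 52.0% for f of 0.503 to 0.48), and less if f is higher.
- *The salt mismatch dilutes the trial's treatment effect.* Holding study drug and giving both arms the same open-label regimen removes the contrast during rescue even if the units match perfectly. No rescue frequency is given, so the effect cannot be sized.
- *Infants now admitted on room-air CPAP will need rescue more often.* The documents give no data on this, and Section 5.1 also requires that relapse not be anticipated.
- *The case report form lacks the needed fields.* Section 5.3 requires documentation of open-label methylxanthine and Section 1.3 has concomitant medications collected throughout. The forms themselves are not in the file.

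**Conclusion.** The point holds as a should-fix inconsistency. Followed as written, the suggested switch lowers the nominal caffeine dose of an active-arm infant by about 50-75% from 36+0 and about 0-50% before. These figures rest on an assumed factor near 0.5. The direction from 36+0 does not depend on that factor, since even at 1:1 the reduction is 0-50%. The realised change is smaller at home if the infant has outgrown the last weight-adjusted dose, and it is gradual in any case.

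This is at odds with the reason given in Sections 1.1 and 4.3 for the step-up, and the fourth step of Section 6.5.1 does not address it. A reader might infer that it must be fixed before the trial can proceed, or that the primary analysis is compromised. The documents support neither: the pathway is discouraged, comes last, and its frequency is unknown.

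**What to change.** 1. Reconcile Sections 1.1, 4.3 and 6.5.1 by stating study drug and open-label caffeine in the same unit (caffeine-base equivalents), with the conversion used, separately for the periods before and from 36+0.
2. Have the clinical and pharmacy leads state whether a lower dose in active-arm infants is intended. This review takes no view on which dose is right and proposes none.
3. Revise the fourth step of Section 6.5.1 so that sites know what the switch does to total caffeine in each arm, as well as whether the rescue dose is safe to give.
4. Optionally, confirm that open-label caffeine is recorded by salt, dose, and start and stop dates, and report rescue days by arm. Leave the primary analysis unchanged.

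The cost is a clarification or amendment centered on one section. The optional item adds a check of an existing record and one descriptive table. No new infants or procedures are needed.

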7 STUDY INTERVENTION DISCONTINUATION AND PARTICIPANT DISCONTINUATION/WITHDRAWAL

7.1 DISCONTINUATION OF STUDY INTERVENTION

The clinical site principal investigators may discontinue the participant's activity without the participant's consent if either of these criteria are met:

- A participant consistently fails to comply with study procedures
- A participant's safety or health may be compromised by further participation

7.2 PARTICIPANT DISCONTINUATION/WITHDRAWAL FROM THE STUDY

Each study participant may withdraw consent at any time during the study without penalty. In the event a participant is discontinued and thus no longer receiving the study drug, the participant will be asked to continue with follow-up assessment as described below, and not considered withdrawn from the study. If the participant refuses further follow-up, then the participant will be considered to be withdrawn. Counseling about the participant's health will be provided if the participant decides to discontinue participation in the study. Medical advice regarding what is in the best interest of the participant will be provided.

All data collected up to the time of withdrawal will be reported. The End of Study eCRF will be completed, with the reason for withdrawal specified.

7.3 LOST TO FOLLOW-UP

- A participant will be considered lost to follow-up if he or she fails to return for the end-of-study visit between 43 weeks + 0 days and 46 weeks and 6 days PMA and is unable to be contacted by the study site staff to (1) reschedule the final visit for the brain MRI (if applicable) to be completed by 46 weeks + 6 days, and (2) return all study equipment and supplies within the next 4 weeks.
- If the subject does not return for the final evaluation, the site will attempt to contact the family and reschedule the missed visit within the next 1-4 weeks, counsel the participant on the importance of maintaining the assigned visit schedule, and ascertain if the family wishes to and/or should continue in the study.
- Before a participant is deemed lost to follow-up, the clinical site investigator or designee will make every effort to regain contact with the participant by multiple means or by contacting designated

alternative contacts. These contact attempts will be documented in the participant's medical record or study file.

- Should the participant continue to be unreachable, the participant will be considered to have withdrawn from the study with a primary reason of lost to follow-up.

8 STUDY ASSESSMENTS AND PROCEDURES

8.1 EFFICACY ASSESSMENTS

8.1.1 OXYGEN SATURATION

Continuous recording of O₂ saturation using the study pulse oximeter is planned for all infants through hospital discharge, **and for the sub-group of infants recruited at hospitals participating in home oximetry recording, will continue through 43 weeks + 6 days PMA (i.e. one week following the last dose of study drug).** The study oximeter will be the Masimo RAD-97, set at the minimum possible averaging time of 2–4 sec and a sampling rate of 1 sec (high resolution). The oximeter will be preset in the sleep lab mode, hence with no “probe off,” “low battery,” or physiologic visual displays or alarms. The internal data storage capacity of the RAD-97 oximeter is sufficient for 28 days of continuous data collection.

Inpatient Phase: During the inpatient phase, the RAD-97 will be a 2nd oximeter, in addition to the one used for standard monitoring in the NICU. Continuous oximeter recordings will be obtained whenever in the NICU. Data will be downloaded from the monitor, and archived by the DCC, at least every 4 weeks while in the NICU and at discharge.

Please note: Some sites may discontinue oximeter recordings at hospital discharge.

Outpatient Phase: **At sites participating in the home oximetry portion of the study,** prior to discharge, the family will be trained in the use of the RAD-97, and will be asked to use the oximeter during all sleep times and quiet awake periods until 43 weeks + 6 days PMA. At home, therefore, we expect at least 8 – 12 hours of use per day, so the memory capacity of the RAD-97 should be sufficient to complete the outpatient phase.

Following discharge, the family will be contacted within the first 2 – 3 days, and then at least weekly to provide support in the use of the study monitor and to support other aspects of the study protocol. As part of their support of the use the monitor at home, study site staff will assess if the use pattern is such that the oximeter memory might be close to capacity, and determine if it is necessary to schedule an additional data download.

8.1.2 INFLAMMATORY BIOMARKERS

An EDTA blood sample (0.6 – 0.8 ml) to measure a panel of inflammatory biomarkers will be obtained at enrollment prior to randomization, and again at 38 weeks + 0 days PMA or NICU discharge, whichever comes first. The blood will be centrifuged and the resultant plasma aliquoted into tubes and immediately frozen (-80 °C). The intent is to freeze a plasma volume of at least 0.3 ml. As specified by later shipping instructions, the frozen samples will be batched and shipped on dry ice overnight using shipping labels that will be provided.

Bulk analyses of inflammatory biomarker plasma concentrations will be performed at Children's National Medical Center using a commercially available ELISA multi-spot assay to measure inflammation-related proteins from different functional categories of cytokines and chemokines, including growth factors, and adhesion molecules, IFN-alpha, IL-6, Gro/CXCL1, IL-1 β , IL-4-6, IL-6 receptor, IL-8, IL-10, IL-13, ICAM-1, myeloperoxidase, CRP, MCP, IGFBP-1, MIP-1a, RANTES, and TNFa. Analytes that show strong trends or significance with this assay may be further analyzed with individual ELISA assays, to confirm the original result.

